9.2. Clinical Laboratory Evaluations

The following hematology, serum chemistry, coagulation, and urinalysis assessments will be performed:

Hematology: Hematocrit, hemoglobin, mean corpuscular hemoglobin, mean corpuscular hemoglobin concentration, mean corpuscular volume, platelet count, red blood cell count, and total and differential leukocyte count

Serum chemistry: Alanine aminotransferase, alkaline phosphatase, aspartate aminotransferase, amylase, lipase, bilirubin (total and direct), blood urea nitrogen, creatinine, random glucose, potassium, sodium, total protein, albumin, and calcium

Coagulation: Prothrombin time, partial thromboplastin time

Urinalysis: pH, protein, glucose, ketone, bilirubin, urobilinogen, blood, nitrite, leucocytes, and specific gravity

A pregnancy test (β -human chorionic gonadotropin) will be performed on all female subjects of childbearing potential at Screening and before each dose administration (urine or serum). A follicle-stimulating hormone test will be performed at Screening, as necessary, to confirm post-menopausal status in female subjects, if not documented in the subject's medical records.

Human immunodeficiency virus (types 1 or 2) antibody, hepatitis B surface antigen, and hepatitis C virus antibody will be assessed at Screening.

A urine screen for drugs of abuse will be performed by the local laboratory at Screening for alcohol, opiates, cocaine, phencyclidine, amphetamines, benzodiazepines, and methadone.

All safety values that have a toxicity score of Grade 1 or greater will also be evaluated by the investigator and classified as "abnormal clinically significant (CS)", or "abnormal not

clinically significant (NCS).” Investigators should use their clinical judgment when considering the clinical significance of any abnormal laboratory findings. All laboratory test values with a toxicity score of Grade 3 or greater will be entered as AEs. Any additional laboratory test value that is determined to be clinically significant will also be recorded as an AE, should that be considered the primary diagnosis. In such instances, the abnormal value and grade will be documented on the AE page of the eCRF. The investigator will continue to monitor the subject with additional assessments until the values have reached the reference range or the values at Screening or until the investigator determines that follow-up is no longer medically necessary. The only exception to this rule would be a laboratory test value that is associated with an identified ongoing AE where that event would be the classifying AE.

All laboratory test results will be presented in the data listings. The results that are outside the reference ranges will be flagged in the data listings. The abnormalities meeting the toxicity grading criteria (Grade 2 or higher) in any safety laboratory will be listed separately. If a subject has a laboratory test with Grade 2 or higher abnormality at any post vaccination visit, then all results for that subject and laboratory test will be presented in the listing.

For hematology, serum chemistry, coagulation, and numeric urinalysis test results, the observed values and changes from Baseline on Days 7, 17, 28 after each vaccination and for sentinel safety subjects also on Day 21 post first vaccination will be summarized by treatment groups as defined in Section 5. These laboratory tests will also be summarized by the toxicity grades.

9.3. Vital Sign Measurements

Vital sign measurements will include systolic and diastolic blood pressures, heart rate, respiratory rate, and body temperature. Vital signs will be measured in Part A at Screening, before and after vaccination on the day of the first vaccination, on Days 1 and 2 (only for sentinel safety subjects), 7, 21 (only for sentinel subjects), and 28 (before second vaccination) post first vaccination, as well as after vaccination on the day of the second vaccination, and on Days 7 and 28 post second vaccination.

If any of the vital sign measurements meet the toxicity grading criteria for clinical abnormalities of Grade 2 or higher, the abnormal value and grade will be documented on

the AE page of the eCRF (unless there is another known cause of the abnormality and that would result in an AE classification).

The vital sign measurements will be presented in a data listing. The values meeting the toxicity grading criteria will be flagged in the data listing. Observed values and changes from Baseline will be summarized by treatment groups as defined in Section 5.

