### **3.5.9        Vital Sign Measurements**

Vital sign measurements will include systolic and diastolic blood pressures, heart rate, respiratory rate, and body temperature (which is classified as a solicited systemic event). The subject will be seated for at least 5 minutes before all measurements are taken. Vital signs will be measured in Part A at the time points indicated in the schedule of events ([Table 6-1](#)).

When procedures overlap and are scheduled to occur at the same time point, the order of procedures should be vital sign measurements and then the blood collection.

Of note, on the day of vaccination, if a subject is noted to have a systolic or diastolic blood pressure, heart rate, or respiratory rate measurement that shows Grade 2 or higher toxicity after 2 measurements (even after relaxing or resting); has an acute illness; or has an oral temperature  $>38^{\circ}\text{C}$ , the subject should not receive a vaccination on that day and will need to return on subsequent days for their vaccination.

If any of the vital sign measurements meet the toxicity grading criteria for clinical abnormalities ([Table 6-3](#)) of Grade 3 or higher, the abnormal value and grade will be documented on the AE page of the eCRF (unless there is another known cause of the abnormality and that would result in an AE classification). The investigator will continue to monitor the subject with additional assessments until the value has reached the reference range,

the value at Screening, is considered stable, or until the investigator determines that follow-up is no longer medically necessary.

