### **3.6.5.2      Safety Analyses**

Data for subjects receiving placebo will be pooled across all dose levels for all presentations. Reactogenicity will be summarized by dose levels (25, 50, or 100 µg or placebo), vaccination (first or second), duration, relationship to study vaccine, and severity. Adverse events will be coded by preferred term and system organ class using MedDRA and summarized by part, treatment, vaccination (first or second), and overall. Adverse events will also be summarized by severity and relationship to study vaccine. Descriptive statistics will be presented and the difference in the proportion of AEs will be provided comparing each dose level with placebo recipients pooled across all dose levels. Adverse events for subjects in the safety cohort for each dose level will be provided in a separate subject listing. Adverse events leading to withdrawal, AESIs, medically attended AEs, and SAEs will be provided by subject in a listing.

Safety data from clinical laboratory test results and vital sign measurements will be graded by severity and analyzed by treatment group and vaccination (first or second). Absolute and change from baseline values will be provided according to the toxicity table, along with mean, median, and standard deviation. Results of hematology, serum chemistry, coagulation, and urinalysis assessments; urine drug screen; and pregnancy testing will be listed for all subjects randomly assigned to receive study treatment.

Medical history data for all subjects randomly assigned to receive study treatment will be presented by subject in a listing.

Baseline demographic and background variables will be summarized by treatment group and cohort for all subjects. The number of subjects who enroll in the study and the number and percentage of subjects who complete the study will be presented. Frequency and percentage of subjects who withdraw or discontinue from the study, and the reason for withdrawal or discontinuation, will also be summarized.

Prior and concomitant medication will be listed (with start and stop dates) for each subject and summarized by common medical dictionary coding. Any vaccinations that occur during the trial conduct will also be captured and summarized.

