mRNA	messenger ribonucleic acid
NCS	not clinically significant
PP	Per-Protocol
PT	preferred term
SAE	serious adverse event
SAS	Statistical Analysis System
SD	Standard deviation
SOC	system organ class
TEAE	treatment-emergent adverse event
TLFs	Tables, listings, and figures
ULOQ	upper limit of quantification
WHODrug	World Health Organization Drug

1. Administrative Structure

This study is being conducted under the sponsorship of Moderna Therapeutics, Inc. The safety and immunogenicity statistical analyses are being performed under contract with PPD in collaboration with Moderna Therapeutics, Inc.

This statistical analysis plan has been written according to protocol VAL-181388-P101, Version 4.0, dated 30 August 2018.

2. Introduction

Chikungunya virus (CHIKV) is a mosquito-borne alphavirus posing a significant public health problem in tropical and subtropical regions. While chikungunya has been present in Africa for centuries, it has recently caused outbreaks and epidemics in new regions reflecting the increasing distribution of the *Aedes* mosquito. A chikungunya epidemic beginning in 2004 in Kenya, which spread to the Indian Ocean islands and to India, and was exported to nearly all regions of the world via infected travelers, resulted in millions of infected individuals and brought chikungunya to the attention of the western world. As of April 2016, chikungunya cases had been reported in 103 countries and territories around the world, including 46 countries and territories throughout the Americas ([Centers for Disease Control and Prevention 2016](#)). There are an estimated 3 million cases of chikungunya globally.

There are currently no effective therapies or approved vaccines to treat or prevent chikungunya, and effective mosquito control has proven challenging, even in higher income countries. Mosquito nets have limited effectiveness against the daytime-biting *Aedes* mosquito. Therefore, there is a need for a safe and effective prophylactic vaccine.

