4.2. Study Endpoints

The following are the safety (primary) endpoints:

Part A:

- Solicited AEs (local and systemic reactogenicity events) collected for 7 days following each vaccination with toxicity grading
- Unsolicited AEs collected for 28 days following each vaccination; additional classification if serious, medically attended, or an AESI
- Safety laboratory test results (serum chemistry, hematology, coagulation, and urinalysis) with toxicity grading
- Vital sign measurements with toxicity grading and physical examination findings

Part B:

- Serious AEs and AESIs through 1 year (or until resolved, whichever occurs first) following the last vaccination

The immunogenicity assessments are as follows:

Part A:

- Serum neutralizing antibody titers to CHIKV proteins (baseline and 28 days after each vaccination)
- Serum binding antibody titers (immunoglobulin G [IgG]) to CHIKV proteins (baseline and 28 days after each vaccination)
- Exploratory antibody assays may be performed with excess serum to assess for cross-reactivity to related viruses at the discretion of the Sponsor

- Additional exploratory assays based upon current research may be performed with excess serum to better characterize the immune response to the CHIKV proteins at the discretion of the Sponsor

Part B:

- Serum neutralizing antibody titers to CHIKV (at 6 and 12 months after the last vaccination)
- Serum binding antibody titers (IgG) to CHIKV-specific proteins (at 6 and 12 months after the last vaccination)
- Exploratory antibody assays may be performed with excess serum to assess for cross-reactivity to related viruses at the discretion of the Sponsor
- Additional exploratory assays based upon current research may be performed with excess serum to better characterize the immune response to the CHIKV proteins at the discretion of the Sponsor

5. General Statistical Considerations

All data collected will be presented in listings. Subjects will be identified in the listings by the subject identification number concatenated with the site number.

Data from subjects excluded from an analysis set will be presented in the data listings but not included in the calculation of summary statistics for the corresponding analysis set.

Data from subjects receiving placebo will be pooled across cohorts for all presentations.

Unless otherwise specified, the following treatment groups will be used for summary purposes:

- 25 µg VAL-181388
- 50 µg VAL-181388
- 100 µg VAL-181388
- Placebo

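### SAP 9.3 and protocol 3.5.9 set different grades for entering vital signs as adverse events, and SAP 9.3 names no summary by grade or vaccination for this graded primary endpoint

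*SAP*

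**What the plan says.** Both documents list vital signs among the primary safety endpoints of Part A, with grading as part of the endpoint: "Vital sign measurements with toxicity grading and physical examination findings" (SAP 4.2; protocol 3.6.1 has the same item).

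They disagree on when a reading goes on the AE page. SAP 9.3 applies "If any of the vital sign measurements meet the toxicity grading criteria for clinical abnormalities of Grade 2 or higher". Protocol 3.5.9 applies at readings "of Grade 3 or higher, the abnormal value and grade will be documented on the AE page of the eCRF". Both make the same exception for a reading explained by another cause that is itself recorded as an AE. SAP Section 1 states: "This statistical analysis plan has been written according to protocol VAL-181388-P101, Version 4.0, dated 30 August 2018". The supplied protocol carries that date.

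On analysis, protocol 3.6.5.2 says: "Safety data from clinical laboratory test results and vital sign measurements will be graded by severity and analyzed by treatment group and vaccination", where vaccination means first or second. SAP 9.3 names two outputs. One is a listing: "The values meeting the toxicity grading criteria will be flagged in the data listing". The other is a summary: "Observed values and changes from Baseline will be summarized by treatment groups as defined in Section 5".

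**The concern.** AE-page entries feed the overall AE summary (SAP 9.1.1) and the table by severity (SAP 9.1.3). A reader of the SAP would take those tables to include every Grade 2 blood pressure, heart rate or respiratory rate reading without another recorded cause. A site working from the protocol need not enter such a reading on grade alone. What the AE counts contain therefore depends on which document was followed.

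The missing grade summary compounds this. If Grade 2 readings are not routinely AEs, a table by grade is the natural place to compare their frequency with placebo, and SAP 9.3 does not name one. With 15 subjects planned at each dose level and 15 on pooled placebo, a group mean change can look flat while a few individuals move into Grade 2.

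**Working it through.** The documents state no figure on this point, so there is none to reproduce. The check sets the passages side by side.

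**1. AE-entry threshold**

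| Data type | Protocol | SAP |
|---|---|---|
| Laboratory values | Grade 3 or above (3.5.8) | Grade 3 or above (9.2) |
| Vital signs | Grade 3 or above (3.5.9) | Grade 2 or above (9.3) |

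The mismatch is confined to vital signs. The readings on which the documents differ are the Grade 2 bands of protocol Table 6-3:

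- systolic pressure 151-155 mm Hg (high) and 80-84 mm Hg (low)
- diastolic pressure 96-100 mm Hg
- heart rate 116-130 (high) and 45-49 (low) beats per minute
- respiratory rate 21-25 breaths per minute

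That is six rows, all affected.

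**2. Analysis by grade and vaccination**

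| Source | By grade | By vaccination |
|---|---|---|
| Protocol 3.6.5.2, laboratory and vital signs | required | required |
| SAP 9.2, laboratory | summary by toxicity grade | days after each vaccination |
| SAP 9.3, vital signs | listing flag only | not stated; treatment group only |

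The protocol sentence covers both data types. The SAP names a grade summary only for the laboratory data.

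**3. Is it covered elsewhere in the SAP?** Section 5 says that categorical variables get frequencies and percentages, and Section 9 says that the toxicity scale is used to categorize vital signs. Neither names an output. Section 9.1.7 summarizes diary oral temperature by vaccination, day and severity, so temperature is covered; blood pressure, heart rate and respiratory rate are not.

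**4. Where sub-threshold readings do show.** There are three places: the listing flags; the minimum and maximum, which SAP Section 5 includes in continuous summaries; and any AE reported on the investigator's judgment (protocol 3.5.7.1 and 3.5.7.2). None gives a systematic count of subjects by grade.

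**5. Assigning the Visit 4 pre-dose reading.** SAP 9.3 places it under the first vaccination ("and 28 (before second vaccination) post first vaccination"). SAP Section 5 computes study day on or after the second-vaccination date as assessment date minus that date, plus 1. The reading is taken on that date, so its study day is 0 + 1 = Day 1 of the second vaccination. A table by vaccination must say which rule governs.

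**6. Unequal numbers of readings.** After the first dose and up to the Visit 4 pre-dose reading, non-sentinel subjects have 3 scheduled occasions (Visit 1 post-dose, Visit 2, Visit 4 pre-dose). Sentinel subjects have 6 (adding Visits 1a, 1b and 3a). After the second dose all have 3 (Visit 4 post-dose, Visits 5 and 7). Each dose group has 3 sentinel subjects in 15, and pooled placebo has 3 × 1 = 3 in 15. A worst-grade comparison between groups is therefore balanced by design. A comparison of first with second vaccination is not quite balanced.

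**The case against.** The strongest reply is that the practical effect is small. Sites follow the protocol, the AE tables count what is recorded, and the SAP sentence only describes data collection. The table shells were not supplied and may include a grade table. Because study day runs from the most recent vaccination, tables by time point would largely separate the doses. The internal safety team and the Safety Monitoring Committee see graded vital signs, and the unblinded interim analyses summarize safety by dose level and pooled placebo.

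Much of this stands as mitigation. It does not supply the missing summary: both committees' reviews are blinded, the routine Safety Monitoring Committee data on vital signs run only through Visit 5, no grade table is named for the interim analyses, and a split by time point shows no grades.

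Four stronger readings are tempting, and the documents do not support them:

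- A reader might infer that ungraded summaries hide these readings entirely, leaving only listing flags. The minimum and maximum show each group's extremes, Grade 1 or 2 readings judged to be AEs are counted, and where another cause explains the reading, that cause is itself an AE.
- A reader might infer that every post-dose Grade 2 reading is a true rise from Baseline, because Grade 2 bars enrollment and vaccination. Those rules apply after two measurements, whereas no repeat is specified post-dose. The bradycardia footnote in Table 6-3 also allows clinical judgment, so a slow resting rate may be unchanged from Baseline.
- A reader might express the gap as a share of grade labels left uncounted. Labels are not subjects, and AE entry by grade is a minimum requirement, so that share measures nothing.
- A reader might infer from the laboratory rule that the SAP sentence is the mistaken one. The eCRF instructions are not available, so the documents do not settle which threshold was intended.

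**Conclusion.** Both parts hold. The SAP and the protocol version it cites contradict each other on the grade at which vital signs enter the AE page, and the passages must be reconciled. SAP 9.3 also does not specify the summary by grade and by vaccination that protocol 3.6.5.2 requires for a graded primary endpoint, although SAP 9.2 specifies one by grade for laboratory tests.

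The extent is the Grade 2 band in six Table 6-3 rows for the threshold, and the absence of a systematic count by grade below whichever threshold applies. No effect size is claimed, because the documents give no Grade 1 or Grade 2 rates. The second part assumes that the unseen shells add no grade table beyond the SAP text. The change should be made before the tables are produced. It does not call the study's design into question.

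**What to change.** Reconcile SAP 9.3 and protocol 3.5.9 to one AE-entry threshold that agrees with the eCRF instructions.

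Add to SAP 9.3 a table of the number and percentage of Safety-set subjects by worst post-vaccination grade, for systolic pressure, diastolic pressure, heart rate and respiratory rate, by treatment group and vaccination, with Baseline grade alongside. Its derivation rule should:

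- keep high and low systolic pressure, and high and low heart rate, apart as in Table 6-3
- take Grades 1 to 3 from measured values (Grade 0 otherwise), and Grade 4 from AE data, because Table 6-3 defines Grade 4 by an emergency visit, hospitalization or intubation
- state how the bradycardia footnote is applied
- state that the Visit 4 pre-dose reading belongs to the first-vaccination period despite the study-day rule in SAP Section 5
- leave out temperature, which Table 6-3 grades as a systemic reaction
- footnote the extra sentinel readings after the first dose

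The cost is one wording edit, one table and a short rule, with no new data. The drawback is noise: some Grade 1 readings (respiratory rate starts at 17 per minute) and single unrepeated Grade 2 readings will be normal variation. The Baseline grade and the placebo column help the reader to judge this.

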- 21. The subject has any abnormality or permanent body art (eg, tattoo) that would obstruct the ability to observe local reactions at the injection site (deltoid region).
- 22. The subject has any condition that, in the opinion of the investigator, would pose a health risk to the subject if enrolled or could interfere with evaluation of the study drug or interpretation of study results (including neurologic or psychiatric conditions deemed likely to impair the quality of safety reporting).
- 23. The subject has a positive test result for hepatitis B surface antigen, hepatitis C virus antibody, or human immunodeficiency virus types 1 or 2 antibodies.
- 24. The subject has a history of active cancer (malignancy) in the last 10 years. An exception is a subject with adequately treated nonmelanomatous skin carcinoma, who may participate in the study.
- 25. The subject has donated blood or blood products  $>450$  mL within 30 days of dosing.
- 26. The subject has any screening vital sign measurement (systolic or diastolic blood pressure, heart rate, or respiratory rate) that shows greater than or equal to Grade 2 toxicity after 2 measurements.
- 27. The subject is an employee or first-degree relative of the Sponsor, PPD, or study site personnel.

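### SAP 9.3 misstates the grade at which a vital sign is recorded as an adverse event (Grade 2 instead of Grade 3) and plans no vital-sign summary by toxicity grade or vaccination

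*SAP*

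**What the plan says.** On recording, protocol 3.5.9 says that a vital sign "of Grade 3 or higher, the abnormal value and grade will be documented on the AE page of the eCRF", unless another known cause accounts for it and is itself the AE. SAP 9.3 repeats this rule with the same exception, but applies it to measurements that "meet the toxicity grading criteria for clinical abnormalities of Grade 2 or higher".

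On analysis, both documents list the endpoint among the primary safety endpoints. SAP 4.2 words it as "Vital sign measurements with toxicity grading and physical examination findings", and protocol 3.6.1 agrees. Protocol 3.6.5.2 says that laboratory results and "vital sign measurements will be graded by severity and analyzed by treatment group and vaccination (first or second". It adds that absolute and change values follow the toxicity table.

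SAP 9.3 plans this: "Observed values and changes from Baseline will be summarized by treatment groups as defined in Section 5". Toxicity grades enter only as flags in the vital-sign listing. For laboratory tests, SAP 9.2 goes further: "These laboratory tests will also be summarized by the toxicity grades".

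**The concern.** Two documents that should state one rule state two. Every reading in the Grade 2 band is an AE under one and need not be under the other. The second gap makes the first matter more. If Grade 2 readings were AEs, the SAP's table of AEs by severity would count them. If they are not, the natural place to count them is a by-grade vital-sign table, and SAP 9.3 does not plan one.

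The primary objective is safety relative to placebo, and the protocol itself gives Grade 2 some weight. It excludes a candidate with a screening vital sign "that shows greater than or equal to Grade 2 toxicity after 2 measurements", and it defers vaccination on the same criterion. At stake is a descriptive count, by arm, of subjects who reach that grade after vaccination.

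**Working it through.** The plan states no figure on this point, so the check is mainly a comparison of text.

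**1. Is the difference left over from an older protocol?** No. The SAP states: "This statistical analysis plan has been written according to protocol VAL-181388-P101, Version 4.0, dated 30 August 2018". The protocol synopsis carries the same date.

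**2. Which grade is the slip?** For laboratory values, protocol 3.5.8 and SAP 9.2 agree on Grade 3 for AE entry. Only the vital-sign sentence in SAP 9.3 differs, which points to a drafting error there.

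**3. Which readings are affected?** The Grade 2 rows of protocol Table 6-3:

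- systolic pressure 80–84 or 151–155 mm Hg
- diastolic pressure 96–100 mm Hg
- heart rate 45–49 or 116–130 beats/min
- respiratory rate 21–25 breaths/min

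Temperature is not affected. Protocol 3.5.9 treats it as a solicited systemic event, and SAP 9.1.7 summarizes those by treatment, vaccination, day and severity.

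**4. What would the SAP show for a Grade 2 reading that is not an AE?** A listing flag (9.3), and the minimum and maximum that SAP section 5 requires for continuous variables. As an illustration, suppose that k of 15 subjects in one dose group fall from 112 to 82 mm Hg systolic, and the others do not change and none is lower.

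- k = 1: mean change −(1 × 30)/15 = −2 mm Hg; minimum 82; minimum change −30.
- k = 2: mean change −(2 × 30)/15 = −4 mm Hg; minimum 82; minimum change −30.

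The extremes are the same in both cases. A by-grade table would give 1/15 = 6.7% and 2/15 = 13.3% (exact 95% interval for 2/15: 1.7% to 40.5%). The AE entries required under the protocol would be 0 in both.

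**5. How many readings are exposed?** From the schedule in SAP 9.3, the readings after the first injection are:

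- after the first vaccination: post-dose, Day 7, Day 28 before the second dose = 3; sentinel subjects add Days 1, 2 and 21 = 6
- after the second vaccination: post-dose, Day 7, Day 28 = 3

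Each group of 15, including pooled placebo, has 12 non-sentinel and 3 sentinel subjects: 12 × 6 + 3 × 9 = 99 readings. Four groups give 396.

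**6. How many subjects might that be?** The documents give no Grade 2 rate, so this is an assumption: 1% to 5% of readings have Grade 2 as the highest grade. Expected subjects per group = 12 × P(at least one in 6) + 3 × P(at least one in 9).

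- Independent readings: at 1%, 12 × 0.0585 + 3 × 0.0865 = 0.96; at 5%, 12 × 0.2649 + 3 × 0.3698 = 4.29.
- Within-subject correlation 0.3 (beta-binomial, assumed): 0.52 to 2.45.
- Within-subject correlation 0.5 (beta-binomial, assumed): 0.38 to 1.80.

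Independence is implausible for repeated blood pressure or heart rate in one person, so its range leans high. All three ranges also ignore the known-cause exception and subjects who reach Grade 3 at another visit.

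**The case against.** The strongest reply is that nothing in the analysis changes. Sites enter AEs under protocol 3.5.7, and the SAP tabulates what they enter. A reader might infer that AE rates by dose depend on which document is followed. The documents do not support that: no SAP step derives AEs from vital-sign values, so the sentence in SAP 9.3 is a wrong restatement of a collection rule. This part of the objection stands.

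A reader might also infer that a Grade 2 signal could go unseen. That too is too strong. Listings flag graded values, the summaries show extremes, and investigators are told to report when in doubt. The internal safety team and the Safety Monitoring Committee also review graded vital signs. Those reviews are blinded, however, so they do not replace a comparison by arm.

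On the missing table, protocol 3.6.5.2 never uses the words by-grade summary, and its explicit comparison with placebo concerns AE proportions. SAP section 9 does say that the toxicity scale will categorize vital signs, and table shells, which are mentioned but not included, may contain such a table. These points lower the certainty that a table is absent. They do not supply one in the SAP text, and a by-grade summary is the fair reading of protocol 3.6.5.2, especially as SAP 9.2 reads it that way for laboratory tests. By-visit tables could separate the two vaccinations in practice, but SAP 9.3 does not say so.

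**Conclusion.** Both defects hold as matters of text. SAP 9.3 gives the wrong grade for AE entry, and it omits the summary by toxicity grade and vaccination for a primary safety endpoint defined with grading. What is lost is a count, by grade and arm, of subjects whose blood pressure, heart rate or respiratory rate reached Grade 2.

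This is a minor SAP correction. Grade 3 or higher reaches the treatment-emergent AE tables under both rules, subject to the shared known-cause exception. The study is descriptive, with 15 subjects per group and no hypothesis test. The conclusion assumes that sites follow the protocol and that no unseen shell already holds the table. It does not depend on the assumed Grade 2 rates.

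**What to change.** 1. In SAP 9.3, change the AE threshold to Grade 3 or higher, as in protocol 3.5.9.
2. Add to SAP 9.3, in parallel with SAP 9.2: *Blood pressure, heart rate and respiratory rate will also be summarized by highest toxicity grade, by treatment group and vaccination (first or second).* The shell should count the pre-dose Visit 4 reading under the first vaccination, as SAP 9.3 already describes it. A separate row for the post-injection reading is optional; the protocol does not ask for it.

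The cost is one numeral, one sentence and one table, in which many cells will be zero. The grades derive from values already scheduled for collection, so no visit, sample, eCRF page or protocol amendment is needed. If a shell already contains the table, only the SAP text needs aligning. Adopting Grade 2 instead would require a protocol amendment, and a return to the AE entries of any subjects already recorded under the Grade 3 rule.
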